6 STATISTICAL AND ANALYTICAL PLANS

The planned tables and listings are presented in Section 8.

Changes in the Planned Analyses 6.1

The SAP presented in this document will supersede the statistical analysis methods described in the clinical protocol. Any deviations/changes from the planned analyses described in this

Sponsor: Laboratorios Salvat, S.A. Study Code: CLOBOF3-16IA01 NCT No.: NCT04246801

document will be identified, with justification, in the appropriate section of the clinical study report (CSR).

Any changes in the statistical analyses once the SAP has been finalised and the database has been locked should be documented at clinical study report (CSR).

VAS is one of the most commonly used measures for pain intensity in clinical trials. In the CLOSE-1 study protocol, eye pain experienced by the subjects at Day 8 compared to placebo is defined as the study's key secondary objective.

Pain is considered a personal and highly subjective experience. The essential requisite for valid interpretation and analysis of VAS ratings obtained throughout the study is to ensure reliable and valid assessments of eye pain.

Different studies (Jensen et al., 2003, Aicher et al., 2011) have been performed to establish preliminary consensus on the cut-offs at which VAS pain scores could be considered no pain, mild, moderate, and severe pain.

Aicher and colleagues categorized VAS pain scores as follows: no pain 0-2 mm, mild pain 2-17 mm, moderate pain 17-47 mm, severe pain 47-77 mm, very severe pain 77-96 mm, and most severe imaginable pain 96-100 mm. On the other hand, Jensen and colleagues concluded that any VAS pain score of 0-4 mm tended to be labeled as no pain.

Based on the previous scientific investigations, the below additional secondary objectives shall be analyzed to complete the evaluation of the eye pain assessment currently described in both, the CLOSE- 1 study protocol and the Statistical Analysis Plan.

These additional analyses shall also help to check the consistency of eye pain assessment by means of a continuous variable (0-100 mm VAS) and its analysis from a dichotomic perspective (no pain VAS=0/pain VAS>0) and from the perspective of the continuous variable the eye pain VAS score is.

- (Proportion of patients with VAS pain score of "0-0.2 cm" (no eye pain) compared to placebo at Day 3, Day 8, Day 15 and Day 29)
- (Proportion of patients with VAS pain score of "0-0.4 cm" (no eye pain) compared to placebo at Day 3, Day 8, Day 15 and Day 29)
- In table 14.2.14 both treatment groups (Clobetasol Propinate/Placebo) at each study visit will be compared using t-test or Mann Whitney Wilcoxon test, as applicable for VAS score.

For FAS non-Rescue and FAS populations.

Additional tables to cover these objectives for both populations 14.2.19.1, 14.2.19.2, 14.2.20.1 and 14.2.20.2 will be added.

6.2 Blind Review

A Blind Data Review Meeting (BDRM) is planned to occur before treatment unblinding takes place. The main objective of this meeting is to review data and identify protocol deviations in order to assign patients to all the analysis sets. Details of BDRM will be specified in a separate document.

A review of all major and critical protocol deviations and their potential consequences for the analysis will be conducted during the BDRM. Results and actions taken will be summarized in the Pre-Analysis Review document, which will be finalized before treatment unblinding.

A summary table will be provided including the number of patients with critical and major protocol deviations and the number of clinical and major protocol deviations. The protocol

Sponsor: Laboratorios Salvat, S.A. Study Code: CLOBOF3-16IA01 NCT No.: NCT04246801

deviations will be listed. The number of patients per study population will be provided. Listings for patients excluded from the SAF, FAS and PP set will be provided.

6.3 Hypotheses and Statistical Methods

6.3.1 Definitions

Baseline	(Visit 1 (Day 1, 24 h after the cataract surgery).				
Time calculation	Differences between dates to express duration will be calculated as the final date - initial date + 1. To convert these days differences to other units, the following conversion factors will be used: 1 year = 365.25 days and 1 month = 30.4375 days.				
	Ex. Age = (informed consent date – date of birth + 1) / 365.25				
Absolute change	Absolute change from Baseline at Visit X will be calculated as:				
from Baseline	Absolute change from Baseline = Visit X - Baseline				
Percentage change	Percentage change from Baseline at Visit X will be calculated as:				
from Baseline	Percentage change from Baseline [%] = ((Visit X - Baseline)/Baseline) *100				
	In case of Baseline = 0 no percentage change from baseline will be calculated.				
Signs of ocular inflammation (yes/no)	The presence/absence of the different signs of ocular inflammation: Chemosis, Bulbar conjunctival injection, ciliary injection, corneal edema, keratic precipitates will be defined as:				
	No: grade=0 (absence)				
	Yes: grade=1, 2 or 3 (presence)				
Conversion Snellen	Step 1. Mar = Snellen Denominator/Snellen Numerator				
to LogMar	Step 2. LogMar = log (Mar)				
	Example: Snellen 20/40				
	Mar = 40/20 = 2				
	LogMar= log(2) = 0.3				
Treatment Emergent Adverse Event	Treatment Emergent Adverse Events (TEAEs) are defined as an event that emerges during treatment having been absent pretreatment or worsens relative to the pre-treatment state:				
	First dose IMP/Pacebo date ≤ start date AE ≤ last dose IMP/Placebo date				
Rescue medication	The following prohibited medications will be considered as rescue medication when administered to subjects not responding to IMP or placebo:				
	 Any systemic or local therapy with corticosteroids (other than the study drug) or immunosuppressant (except pre- surgical and/or surgical administration of 1 drop of a topical NSAID or corticosteroid, at the investigator discretion) 				

Date: 09-JUL-2021

Sponsor: Laboratorios Salvat, S.A. Study Code: CLOBOF3-16IA01

NCT No.: NCT04246801

	 Any topical ocular medication (except preservative-free antibiotics for prophylactic purposes and preservative-free artificial tears) Any systemic NSAID or opioids drugs (except occasional use of OTC formulations titrated no more than one single dose per week) 			
Relative day	The relative day of an event that occurs prior to administration of IMP:			
	Relative day = (Start date)-(Date of administration of IMP).			
	The relative day of an event that occurs on the same day or after administration of IMP:			
	 Relative day = (Start date)-(Date of administration of IMP)+1. 			
	Consequently, Day 1 is the same day as the day of administration of IMP, Day -1 is the day before, and Day 2 is the day after.			

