7.4 Secondary Safety Endpoints

The secondary safety endpoints will be:

- Number, frequency and severity of AEs up to Day 29
- Number, frequency and severity of Serious AE (SAE) up to Day 29
- Proportion of patients discontinuing the study due to AEs
- Proportion of patients discontinuing the study due to lack of efficacy
- Change from Baseline to Day 3, Day 8, Day 15 and Day 29 compared to placebo in IOP
- Change from Baseline to Day 3, Day 8, Day 15 and Day 29 compared to placebo in physical and eye examination parameters and vital signs
- Use of concomitant medications up to Day 29

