9.1.13 Safety Analyses

The total number of patients with at least one AE and the total number of AEs will be presented. The number of patients and the number of AEs overall and in each by randomized treatment group will be tabulated by SOC and by PT. AEs will also be tabulated versus worst severity and worst relationship to treatment. In this table, patients with AEs will be identified by their patient number.

The number of patients with TEAEs and the number of TEAEs overall and in each sub-set will be tabulated by SOC and PT. Frequency tables for the overall population and by each sub-set will also be presented for TEAEs related to study drug, TEAEs leading to study drug discontinuation, TEAEs of special interest, serious TEAEs (STEAEs), and STEAEs related to study medication. Additional summary tables will be provided for TEAEs with worst severity by SOC and PT per patient and TEAEs with worst relationship by SOC and PT per patient.

Listings of patients with STEAEs, deaths and STEAEs leading to discontinuation and individual narrative summaries for these cases will be provided. In the listings, patients with TEAEs will be identified by their patient number.

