3.3 Secondary Safety Endpoints

- Number, frequency and severity of adverse events (AEs) up to Day 29.
- Number, frequency and severity of serious AEs (SAEs) up to Day 29.
- Proportion of patients discontinuing the study due to AEs.
- Proportion of patients discontinuing the study due to lack of efficacy.
- Change from Baseline to Day 3, Day 8, Day 15 and Day 29 compared to placebo in intraocular pressure (IOP).
- Change from Baseline to Day 3, Day 8, Day 15 and Day 29 compared to placebo in physical and eye examination parameters and vital signs.
- Use of concomitant medications up to Day 29

The IOP will be assessed in both eyes using the Goldmann applanation tonometry method (for details see Appendix 3 of CSP).

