6.3.10 Adverse Events

AEs data are collected on the 'Adverse Events' eCRF form.

AEs will be coded according to the Medical Dictionary for Regulatory Activities (MedDRA) system, the latest version and tabulated by System Organ Class (SOC) and by Preferred Term (PT).

A Treatment-Emergent Adverse Event (TEAE) is defined as an AE observed after starting administration of IMP or placebo (see Section 6.3.1).

TEAEs will be summarized by presenting, for each treatment regimen, the number of events and the number and percentage of patients with:

Study Code: CLOBOF3-16IA01 Date: 09-JUL-2021 NCT No.: NCT04246801

Sponsor: Laboratorios Salvat, S.A.

- Any TEAE
- Any Serious Treatment Emergent Adverse Event (STEAE)
- Any TEAE of Special Interest (TEAESI)
- Any TEAE related to IMP/Placebo
- Any TEAE leading to treatment discontinuation (drug withdrawn)
- Any STEAE related to IMP/Placebo
- Any TEAESI related to IMP/Placebo

The number and percentage of TEAEs by causality and the number and percentage of mild moderate and severe TEAEs will be tabulated by SOC, PT and treatment arm. All tables with TEAEs by SOC and PT stratified by treatment regimen will only be counted by patient once within each PT.

The following tables will be provided with TEAEs by SOC and PT stratified by treatment regimen: TEAEs, TEAEs related to IMP/Placebo, TEAEs leading to discontinuation, STEAEs, STEAEs related to IMP/Placebo, TEAESI and TEAESIs related to IMP/Placebo.

TEAEs, STEAEs and TEAESIs will be tabulated by severity (mild, moderate or severe) and relationship to treatment (No: not related, unlikely related, Yes: possible, probable and certain). If a patient has more than one event with the same PT, the AE will only be counted once and the worst/maximal severity and the worst/strongest relationship will be used.

A listing of all AEs will be presented, whether treatment emergent or not. TEAEs will be flagged in this listing. A separate listing for deaths, STEAEs, AESIs and TEAEs leading to discontinuation will be provided (if any).

The following AEs (SOC, PT) of special interest (AESI) will be evaluated by Investigators at all study visits and time points (as applicable):

- IOP rise over 30 mmHg (SOC- INVESTIGATIONS, PT-INTRAOCULAR PRESSURE INCREASED)
- Pain/discomfort associated with IMP instillation (SOC-EYE DISORDERS, PT-EYE PAIN, OCULAR DISCOMFORT and related with IMP)

Additionally, a descriptive table (14.3.1.2.2) of ocular adverse events will be presented by SOC and PT.

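### Every planned adverse-event table stops at the last dose, so the Day 29 safety endpoint is not tabulated by arm after treatment ends

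*SAP*

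**What the plan says.** The first safety endpoint in SAP 3.3 is "Number, frequency and severity of adverse events (AEs) up to Day 29". Protocol 7.4 has the same: "Number, frequency and severity of AEs up to Day 29". A parallel endpoint covers serious AEs over the same period.

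SAP 6.3.1 gives the only definition of a TEAE that contains dates: "First dose IMP/Pacebo date ≤ start date AE ≤ last dose IMP/Placebo date". No days are added after the last dose.

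SAP 6.3.10 is worded differently. It says that AEs, not only TEAEs, will be tabulated by SOC and PT. It then states that "A Treatment-Emergent Adverse Event (TEAE) is defined as an AE observed after starting administration of IMP or placebo", with no end date, but refers the reader back to 6.3.1. For everything else it promises a listing: "A listing of all AEs will be presented, whether treatment emergent or not".

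Protocol 9.1.13 planned more than this. Before it turns to TEAEs, it says that "the number of AEs overall and in each by randomized treatment group will be tabulated by SOC and by PT". SAP 6.1, however, says: "The SAP presented in this document will supersede the statistical analysis methods described in the clinical protocol".

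**The concern.** The endpoint covers the whole follow-up to Day 29, but the tables meant to deliver it cover only the dosing period. SAP 6.3.10 says that the arms will be compared on safety only descriptively, so the by-arm tables are the safety comparison. For events that start after dosing ends there is no by-arm AE count, neither of events nor of patients.

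The AE of special interest (AESI) most exposed is an IOP rise over 30 mmHg; the other AESI, pain or discomfort on instillation, is tied to dosing. Protocol 8.3.9 has AESIs evaluated at all study visits, and IOP is measured at Visit 5. An IOP AESI with onset at Visit 5 would still enter neither Table 14.3.1.9 nor Table 14.3.1.10.

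The window can also differ between patients. Under Protocol 6.7.2 a rescued patient stops study drug, which moves the last-dose date, and with it the end of AE counting, earlier. If rescue is more frequent in one arm, that arm has a shorter counting period. The documents give no rescue rates, so no size can be put on this.

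**Working it through.** **Last-dose date.** SAP 6.3.8 states 56 planned doses, which reproduces: 4 per day × 14 days = 56. There are two readings of when dose 56 falls.

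- Four doses on each of 14 consecutive days from Day 1: last dose on Day 14.
- One clinic dose plus 55 dispensed vials (Protocol 6.2), about 6 hours apart (Protocol 6.2.2): dose 56 comes 55 × 6 h = 330 h = 13 days 18 h after dose 1. If dose 1 is given at or after 06:00 on Day 1, that is Day 15.

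**Days outside the window, to Day 29.**

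- Last dose on Day 14: 29 − 14 = 15 days; 15/29 = 51.7%.
- Last dose on Day 15: 29 − 15 = 14 days; 14/29 = 48.3%.
- Visit 5 may fall on Days 27 to 31. With the last dose on Day 14 the share runs from 13/27 = 48.1% to 17/31 = 54.8%.
- Early stop, for illustration only: last dose on Day 3 gives 26/29 = 89.7%; last dose on Day 8 gives 21/29 = 72.4%.

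**AE tables in SAP 8.1.**

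- TEAEs: 14.3.1.1, 14.3.1.2.1, 14.3.1.2.2 and 14.3.1.3 to 14.3.1.6, which is 7.
- Serious TEAEs: 14.3.1.7 and 14.3.1.8, which is 2.
- TEAEs that are AESIs: 14.3.1.9 and 14.3.1.10, which is 2.
- Total 7 + 2 + 2 = 11. Tables that can include onset after the last dose: 0 of 11.

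**Where later events appear.** They are in the AE listing (16.2.7.1) and, for deaths, serious and other significant events, in item 14.3.2, which is titled as listings. SAP 6.3.3 sorts listings by centre and patient number. Protocol 9.1 labels them by randomized group, so counts by arm could be recovered, but only by hand.

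**IOP checks outside the window.** The scheduled post-baseline checks are Visits 2, 3, 4 and 5, so 4. Visit 5 is always after the last dose: at least 1 of 4. Visit 4 may fall on Day 15 − 2 = 13 to Day 15 + 2 = 17. It is also outside on Days 15 to 17 if the last dose is on Day 14, and on Days 16 to 17 if it is on Day 15. It is then 2 of 4.

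**What the IOP table adds.** Table 14.3.4.2 summarises IOP by arm to Day 29. The statistics in SAP 6.3.2 for continuous data include a maximum, but no number of patients above 30 mmHg.

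**The case against.** Five points can be made in the plan's favour.

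- *On-treatment windows are ordinary practice.* True, and the definition is not wrong in itself. The fault is that it is the only basis for the AE tables while the endpoint runs to Day 29.
- *SAP 6.3.10 has no end date, and on that wording all 11 tables would reach Day 29.* The two sections do conflict. But 6.3.10 points to 6.3.1, which alone has a rule that can be programmed, so the narrower reading is the likelier one. If a programmer took the other reading, the content of all 11 tables could change. That is a reason to settle the wording.
- *Other outputs reach past the last dose.* Tables 14.3.10.2 and 14.3.10.3 would show medication given for a late event. Table 14.1.3 gives reasons for leaving the study early. An IOP maximum of 30 mmHg or less in an arm would show that no summarised reading there was higher. These are real but partial substitutes: none counts AEs, and an untreated event would be missed by the medication tables.
- *SAP 6.3.10 also promises a separate listing that includes AESIs.* So late IOP events can be found without searching all AEs, and in a trial of about 210 patients a hand count is feasible. It remains a listing, without counts or percentages by arm.
- *The percentages measure calendar time, and a rise found at Visit 4 may be given an earlier start date.* Both stand. The figures do not say how many events are lost from the tables, and no bias between arms has been shown.

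**Conclusion.** The concern holds. Followed as written, the SAP does not tabulate its own AE and serious-AE endpoints by arm over the stated period, and it has no table for the all-AE tabulation in Protocol 9.1.13.

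The gap is 14 to 15 of 29 days (48% to 52%) for a patient who completes dosing, 0 of 11 AE tables with post-dosing onset, and 1 or 2 of 4 scheduled post-baseline IOP checks. This assumes that 6.3.1 governs, that the last dose falls on Day 14 or 15, and, for the IOP checks, that an event is dated to the visit at which it is found.

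No data are lost and the efficacy analyses are unaffected. This should be fixed, but it does not threaten the trial's main conclusion.

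**What to change.** - Reconcile SAP 6.3.1 with 6.3.10 so that one TEAE definition, with explicit start and end, applies throughout.
- Keep the on-treatment TEAE tables if they are wanted.
- Add by-arm tables in the safety set for AEs, serious AEs and AESIs with onset after the last dose through Visit 5 (nominal Day 29), and a by-arm total from first dose to the same point. State the cut-off precisely, since Visit 5 may be as late as Day 31.
- In both sets, flag events that start after rescue. Rescued patients stop study drug and may receive corticosteroids, so those events should not be read as on-drug events.

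The cost is SAP wording, two derived flags (onset after last dose, onset after rescue) and a few safety tables. AEs are already collected to Visit 5, so no new data are needed. The drawback is that total AE counts will be higher, and post-treatment counts must be read separately from on-drug counts.

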8.3.1 Definitions

8.3.1.1 Adverse Event (AE)

An AE is defined as any untoward medical occurrence in a patient or clinical trial patient administered a medicinal product and which does not necessarily have a causal relationship with this treatment.

An AE can therefore be any unfavorable and unintended sign (including an abnormal laboratory finding), symptom, or disease temporally associated with the use of an IMP, whether or not considered related to the IMP.

Medical disorders present at the time of the first administration of IMP are only considered AEs if they significantly worsen after this time. All baseline conditions should be recorded as part of the Medical History.

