8.3.2 Timing

Adverse events will be recorded from the time of informed consent completion, throughout the study, and at early termination. Adverse events that were on-going when the patient completed the study will continue to be followed until resolution or until the investigator decides that the AE is stable; AEs will be coded using the MedDRA dictionary.

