8.3.3 Recording Adverse Events

Volunteered, observed, and elicited AEs will be recorded. This includes AEs the patient reports spontaneously, those the investigator observes, and those the elicited in response to questions from the study staff. Patients will be asked open-ended questions, such as "How have you been feeling since your last visit?", at each study visit.

All AEs that occur during the study must be recorded in the AE section of the eCRF. All AEs eCRF entries should contain a brief description of the event, date and time of onset, duration, intensity, treatment required, relationship to study medication, action taken with regard to study medication, outcome, and whether the event is classified as serious.

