8.3.4.1 Severity

Severity describes the intensity of an event. The severity of each AE must be assessed by the investigator and recorded on the eCRF as mild, moderate or severe according to the following definitions:

Mild: The AE does not interfere in a significant manner with the patient's normal functioning level. It may be an annoyance.

Moderate: The AE produces some impairment of function or it interferes with usual activities but not hazardous to health. It is uncomfortable and/or an embarrassment.

Severe: The AE produces significant impairment of functioning or incapacitation and/or it is a hazard to the patient. An AE that is assessed as severe should not be confused with a SAE. Severe is a category utilized for rating the intensity of an event; and both AEs and SAEs can be assessed as severe.

If an AE changes in severity, the worst severity should be reported.

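### The TEAE formula in SAP 6.3.1 omits the worsening limb of its own definition and cannot separate pre-dose from post-dose onset on Day 1

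*SAP*

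**What the plan says.** SAP 6.3.1 states the TEAE definition twice in one table cell. In words, a TEAE is "an event that emerges during treatment having been absent pretreatment or worsens relative to the pre-treatment state". The rule beneath it is a date comparison: "First dose IMP/Pacebo date ≤ start date AE", closed at the other end by "start date AE ≤ last dose IMP/Placebo date". SAP 6.3.10 refers back to 6.3.1 but words it a third way: a TEAE "is defined as an AE observed after starting administration of IMP or placebo".

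The protocol decides which records reach that rule:

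- Section 8.3.2: "Adverse events will be recorded from the time of informed consent completion". Surgery (Day -1) falls between consent and the first dose (Day 1).
- Section 8.3.4.1: "If an AE changes in severity, the worst severity should be reported". Nothing is said about opening a new record or entering a date of worsening.
- Section 8.3.1.1: "Medical disorders present at the time of the first administration of IMP are only considered AEs if they significantly worsen after this time". The same section sends baseline conditions to Medical History.
- Section 8.3.3 asks for "date and time of onset", while 8.3.7 asks for the start time only where relevant.
- Section 4.3.2.2 keeps expected changes after routine surgery out of the AE data. It lists the Visit 1 eye examinations before the first dose and the AE assessment after it.

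In SAP 8.1, AE summary tables 14.3.1.1 to 14.3.1.10 are all TEAE tables. Protocol 9.1.13 also planned tabulations of all AEs by randomized group, but SAP 6.1 says the SAP supersedes the protocol's statistical methods.

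**The concern.** A programmer will code the formula, and the formula does not implement the sentence above it. Two kinds of record are affected.

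The first is an AE entered after consent, with onset before the first dose, that worsens on study drug. By the wording it is treatment-emergent. By the formula it is not, if the record keeps its original start date. It would then be absent from every by-arm AE count and visible only in the listing of all AEs. The drug is a steroid eye drop started the day after surgery, so on-drug worsening of an early post-operative event is something the safety tables ought to show.

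The second is an AE entered with a Day 1 onset that precedes the first dose. First dose and onset share a calendar date, so the rule counts the event, although it was present before treatment and has not worsened.

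In both situations the classification depends on how a site happens to date the record, not on a stated rule.

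**Working it through.** The plan gives no figure to reproduce here, so the check applies the rule to hypothetical records. First dose is taken as Day 1 and last dose as Day 14, assuming a full course. The formula is met when first-dose date ≤ AE start date ≤ last-dose date. The wording is met when the event is new on treatment, or was present before treatment and worsens.

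| Record | Formula | Wording |
|---|---|---|
| A. AE starts Day -3, worsens Day 5, one record with its original date | No | Yes |
| B. AE starts Day -1, found at the pre-dose Day 1 examination, no worsening | No | No |
| C. AE dated Day 1, before the first dose, no worsening | Yes | No |
| D. AE dated Day 1, before the first dose, worsens Day 5 | Yes | Yes |
| E. Pre-existing disorder whose worsening is entered as an AE starting Day 5 | Yes | Yes |

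The two definitions disagree on A and C.

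Record A can arise. AE recording begins at consent, and the SAP expects some AEs that are not treatment-emergent, because it plans a listing of all AEs with TEAEs flagged. A and E may describe the same clinical course and differ only in the date entered. Protocol 8.3.4.1 settles the severity to report but not the date, and 8.3.1.1 makes worsening the qualifying condition without saying that the AE then starts at the worsening.

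Record C arises only if an item is entered as an AE with a Day 1 onset before dosing. SAP 6.3.1 sets Day 1 as the date of first administration, so a date-only comparison cannot separate C from an event that began after the drop was given. SAP 6.3.10 requires that dosing has started, and the 6.3.1 wording requires that the event was absent beforehand or has worsened. C meets neither requirement.

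Neither document gives a rate for AEs with pre-dose onset, for the share of these that worsen, or for AEs dated Day 1 before dosing. No count of affected patients can be derived.

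**The case against.** The strongest reply is that the protocol keeps most such items out of the AE data. Under 8.3.1.1 a disorder present at first dose belongs in Medical History and becomes an AE only through later worsening. If the worsening date is entered as the start date, the formula counts it (record E). Expected surgical inflammation and pain are not AEs, and the Visit 1 AE assessment is listed after dosing. All AEs are listed. IOP change is tabulated by arm whatever the TEAE status (table 14.3.4.2), as is the severity of ocular signs (tables 14.2.11.1 to 14.2.11.10). The same rule applies to both arms, and SAP 6.3.10 makes the safety comparison descriptive only.

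Most of this stands, and it limits the size of the problem. It does not remove the contradiction. Section 8.3.1.1 makes worsening the criterion, which is the limb the formula lacks, and no section says which start date to use. The IOP and ocular-sign tables cover only those measures, and the ocular-sign tables use the analysis set that leaves out rescued patients.

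A reader might infer two stronger claims that the documents do not support:

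- That on-treatment worsening of a pre-dose event is never counted. Record E shows that it is counted when the worsening is dated as such. That a changing AE must stay one record at its first date is an inference, since 8.3.4.1 speaks only of severity.
- That whatever is found at the pre-dose Day 1 examination becomes treatment-emergent. The formula uses the AE start date, not the date of finding, so a finding dated to surgery fails it (record B). Only an item entered as an AE with a pre-dose Day 1 onset passes.

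**Conclusion.** The point holds in limited form. The SAP 6.3.1 formula contradicts the definition directly above it by leaving out worsening, and its date-only comparison admits pre-dose Day 1 onsets that 6.3.10 would exclude. This is an error in a stated rule, not missing detail, and it governs every by-arm AE summary table.

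The effect is probably small, though this is a judgement from the protocol's recording rules and not a calculation. It assumes that sites follow 8.3.1.1 and 4.3.2.2, so that few AEs carry an onset before the first dose. Any percentage of patients attached to the problem would have no basis in the documents.

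**What to change.** In SAP 6.3.1, replace the lower bound of the rule. A TEAE should be an AE with onset after the first dose, or with onset before the first dose and worsening after it. Align 6.3.10 with the same words. The end of the window is a separate question that this change does not address.

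- **Dating.** State that a post-dose worsening of a pre-dose event is dated at the worsening.
- **Blind review.** At the blind data review already planned in SAP 6.2, examine every AE with pre-dose onset for on-treatment worsening, and record the classification before unblinding.
- **Day 1.** Compare onset time with first-dose time where both are recorded. If the time is missing, count the event as a TEAE. Because 8.3.7 asks for time only where relevant, some Day 1 events will stay classified as they are now, which errs towards inclusion.

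The cost is minor SAP wording and programming, and a blinded review of what should be a few records. As only the worst severity is reported, some may need a query to the site to establish when the worsening occurred. A new eCRF field is not needed.
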